12.4.2 Increase in Autoimmune Disease Activity

Any increase in autoimmune disease activity (flare/relapse) for the participant's qualifying autoimmune disease will not be reported as an AE. These events will be collected and reported on the disease-specific assessment eCRFs. (Section 8.1.4.2 Disease-Specific Assessments).

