12.2.5 Adverse Events of Special Interest

Adverse events of special interest (AESIs) include the following:

- Myocarditis (probable and confirmed cases)
- Pericarditis

See Appendix 20.8 for cases definitions of probable and confirmed myocarditis and pericarditis according to the Centers for Disease Control and Prevention (CDC) criteria

In addition, the following AESI will be collected in the arms in which the Sanofi-GSK COVID-19 Vaccine is administered.

- New onset of potential immune-mediated diseases (pIMDs).

See Appendix 20.7. Disease flares of the underlying autoimmune disease, including new manifestation of the disease will not be captured as an AESIs. Disease flares should be reported following Section 12.4.2 Increase in Autoimmune Disease Activity.

pIMDs are a subset of AEs that include autoimmune diseases and other inflammatory and/or neurologic disorders of interest which may or may not have an autoimmune etiology. AEs that need to be recorded and reported as pIMDs, including those listed in Appendix 20.7.

However, the Investigator will exercise their medical and scientific judgment in deciding whether other diseases have an autoimmune origin (that is pathophysiology involving systemic or organ-specific pathogenic autoantibodies) and should also be recorded as a pIMD. When there is enough evidence to make any of the diagnoses mentioned in Appendix 20.7 the AE must be reported as a pIMD. Symptoms, signs or conditions which might (or might not) represent the above diagnoses, should be recorded and reported as AEs but not as pIMDs until the final or definitive diagnosis has been determined, and alternative diagnoses have been eliminated or shown to be less likely.

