12.2.6 Serious Adverse Event (SAE)

An AE or SAR is considered “serious” if, in the view of either the investigator or Sponsor (DAIT/NIAID), it results in any of the following outcomes (21 CFR 312.32(a)):

1. Death.

2. A life-threatening event: An AE or SAR is considered “life-threatening” if, in the view of either the investigator or Sponsor [add DAIT/NIAID or other Sponsor, *if applicable*], its occurrence places the participant at immediate risk of death. It does not include an AE or SAR that, had it occurred in a more severe form, might have caused death.
3. Inpatient hospitalization or prolongation of existing hospitalization.
4. Persistent or significant incapacity or substantial disruption of the ability to conduct normal life functions.
5. Congenital anomaly or birth defect.
6. Important medical events that may not result in death, be life threatening, or require hospitalization may be considered serious when, based upon appropriate medical judgment, they may jeopardize the participant and may require medical or surgical intervention to prevent one of the outcomes listed above.

Elective hospitalizations or hospital admissions for the purpose of conduct of protocol-mandated procedures are not to be reported as an SAE unless hospitalization is prolonged due to complications.

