12.4 Collection and Recording of Adverse Events

12.4.1 Collection Period For All Cohorts

For this study, the timelines below apply after each study-administered vaccine:

- Solicited AEs (all grades) will be collected from Day 1 (vaccine administration) through 7 days post study vaccination.
- Unsolicited AEs will be collected as follows:
 - Any unsolicited AEs that are Grade 3 or higher will be collected from randomization/allocation through vaccination administration.
 - All unsolicited AEs (all grades) will be collected from Day 1 through Day 28.

- Any flares of a secondary autoimmune disease will be reported as an unsolicited AE (all grades) and will be collected from Day 1 through the end of the participant's study participation.
- AESIs will be collected as follows:
 - Pericarditis/myocarditis events will be collected in all treatment arms. NCI-CTCAE Grade 2 or higher myocarditis and pericarditis events from Day 1 through the end of the participant's study participation.
 - New onset of pIMDs will only be collected in arms where the Sanofi-GSK COVID-19 Vaccine is administered. All grades will be collected from Day 1 through the end of the participant's study participation.
- SAEs, MAAEs, and NOCMCs will be collected from Day 1 through the end of the participant's study participation, regardless of NCI-CTCAE grade.
- COVID-19 diagnoses (all grades) confirmed by molecular COVID-19 testing will be collected from Day 1 through the end of the participant's study participation.

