12.5.2 Reporting Serious Adverse Events

This section describes the responsibilities of the site investigator to report SAEs and AESIs to the sponsor via the eCRF. Timely reporting of AEs is required by 21 CFR and ICH E6 R2 guidelines.

Site investigators will report all SAEs (see Section 12.2.6 Serious Adverse Event (SAE)) and AESIs (see Section 12.2.5 Adverse Events of Special Interest), regardless of relationship or expectedness within 24 hours of discovering the event.

For SAEs and AESIs, all requested information on the AE/SAE eCRF will be provided. However, unavailable details of the event will not delay submission of the known information. As additional details become available, the AE/SAE eCRF will be updated and submitted.

When a site investigator identifies an SAE or AESI specified above, he or she must notify DAIT/NIAID via the DAIT-SACCC within 24 hours. Site investigators are to report these events on the SAE eCRF in EDC. Should EDC become unavailable/inaccessible, the site investigator should notify DAIT/NIAID via the DAIT-SACCC email at [contact]. This email can serve as the initial notification; however, within the next business day, the SAE eCRF must be completed.

All requested information on the SAE eCRF should be provided. Unavailable details of the event at time of initial report should not delay submission of known information. The initial report should include at a minimum: AE term, relationship to vaccine, and reason why event is serious (per definitions). Supplementary CRF pages including medical history, concomitant medications, demographics, study drug administration, and death must be provided. As additional details become available, the SAE eCRF should be updated and submitted. Each SAE or AESI must be signed by the investigator in the EDC system at the time of initial submission and upon SAE or AESI closure. If an SAE or AESI is determined to require an expedited report to a Health Authority, then the SAE or AESI will be signed by the investigator on a more frequent basis. With each iteration of the form, the investigator (or designated sub-investigator) must sign the form electronically.

For additional information regarding SAE reporting, contact Rho Product Safety (DAIT-SACCC):

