12.5.4 Mandatory reporting to Vaccine Adverse Event Reporting System

Per the FDA EUA for the Pfizer-BioNTech COVID-19 Vaccine, FDA EUA for the Moderna COVID-19 Vaccine, the FDA EUA for the Janssen COVID-19 Vaccine, the site investigator or designee is responsible for mandatory reporting of the following to the Vaccine Adverse Event Reporting System (VAERS) [48, 58, 59]:

- Vaccine administration errors, whether or not associated with an AE,
- SAEs (irrespective of attribution to vaccination),

- Cases of Multisystem Inflammatory Syndrome in adults and children, and
- Cases of COVID-19 that result in hospitalization or death.

Vaccination providers may report to VAERS other AEs that are not required to be reported.

The site investigator, or designee, is also responsible for recording vaccination information in the state/local jurisdiction's Immunization Surveillance System or other designated system.

12.5.5 Reporting of Adverse Events to Institutional Review Boards (IRBs)/Institutional Ethics Committees (IECs)

All investigators shall report AEs and SAEs, including expedited reports, in a timely fashion to their respective local IRBs and single IRB in accordance with applicable regulations and guidelines. All safety reports to the FDA shall be distributed by the Sponsor (DAIT/NIAID) or designee to the single IRB and all participating institutions for local IRB submission if required.

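### Section 12.4.2 removes flares of the qualifying disease from AE reporting with no exception for serious ones, so serious flares after the 7-day diary window can miss the SAE endpoint and 24-hour reporting

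*Protocol*

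**What the plan says.** Protocol Section 12.4.2 states that any rise in activity of the participant's "qualifying autoimmune disease will not be reported as an AE". Instead, "These events will be collected and reported on the disease-specific assessment eCRFs". The section gives no deadline and no exception for seriousness.

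Section 12.2.6 defines an SAE as an AE or suspected adverse reaction that, "in the view of either the investigator or Sponsor (DAIT/NIAID), it results in any of the following outcomes"; one of those outcomes is "Inpatient hospitalization or prolongation of existing hospitalization". Section 12.5.2 requires sites to report SAEs and AESIs "regardless of relationship or expectedness within 24 hours of discovering the event". Section 12.2.5 closes the AESI route: "Disease flares of the underlying autoimmune disease, including new manifestation of the disease will not be captured as an AESIs".

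Two other provisions treat disease worsening differently. Section 12.2.1.3 lists worsening symptoms of the underlying autoimmune disease among the solicited AEs, and Section 12.5.1 requires a solicited AE that is also an SAE to be entered in EDC. Section 12.4.1 makes a flare of a secondary autoimmune disease an unsolicited AE of any grade, collected to the end of participation.

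The safety endpoint in Section 3.3 counts SAEs, MAAEs and NOCMCs; flares are a separate set of secondary endpoints.

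**The concern.** Withholding MMF/MPA or MTX is the randomised comparison in Stage 1 Cohorts A and B. In Stage 2 it is required in Cohorts D and E, and for any Cohort F participant taking those drugs (Section 7.1.1). Section 5.3.1 names disease exacerbation and flare as its risk. The most serious form of that harm is a flare that puts a participant in hospital, and Section 12.4.2 is silent on what a site should do with one.

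Two things are at stake. The sponsor may not hear of a serious flare within 24 hours. And the SAE tables, which SAP Section 9.3 presents by treatment group, may leave out the events most closely tied to the withholding plan, or include them at some sites and not at others. Adult Stage 1 is closed to enrolment, but Pediatric Stage 1 still randomises and Stage 2 still withholds.

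**Working it through.** The plan states no figure on this point, so the check sets the provisions side by side. The arithmetic at the end only shows what the DSMB flare trigger can and cannot do.

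**Reporting routes for a serious flare of the qualifying disease**

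1. *AE form.* Closed by 12.4.2.
2. *SAE form.* By 12.2.6 an SAE is an AE or a suspected adverse reaction, and 12.2.1.1 makes the latter a kind of AE. If the flare is not handled as an AE, nothing carries it to the SAE form.
3. *AESI.* Closed by 12.2.5.
4. *VAERS.* Section 12.5.4 covers SAEs whatever their attribution, so it depends on step 2.
5. *MAAE.* Section 12.2.4 requires at least a possible relation to the vaccine. A hospitalised flare attributed to stopping the drug does not qualify.
6. *Medical Monitor's monthly report.* Section 12.8.1 lists AEs, AESIs, SAEs, MAAEs, NOCMCs and pregnancies, and no flare category.
7. *Solicited AE.* Open under 12.2.1.3 and 12.5.1, but 12.4.1 limits it to Day 1 through 7 days after vaccination.

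**How far the solicited window reaches**

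- The MMF/MPA hold runs 10 days after vaccination (7.1.1), so 10 − 7 = 3 days of the hold lie beyond the window. MTX may be held for up to 21 days in total.
- The protocol's own period for a severe flare is 12 weeks (12.8.2.2), or 84 days. About 84 − 7 = 77 of those days, 92%, lie beyond the window. This is a share of time, not of flares.

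**What the DSMB trigger offers instead**

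The trigger is a severe flare within 12 weeks in 3 of the first 10 participants, or 30% after that. The documents give no severe-flare rate, so the true rate p is assumed:

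P(at least 3 of 10) = 1 − Σ C(10,k) p^k (1−p)^(10−k), k = 0, 1, 2

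| assumed p | chance of reaching 3 of 10 |
|---|---|
| 5% | 1.2% |
| 10% | 7.0% |
| 15% | 18.0% |
| 20% | 32.2% |
| 30% | 61.7% |

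The text sets the 30% rule by stage and does not say by arm. If it is pooled over Stage 1 and all planned arms fill, withhold arms hold 6 × 60 / 900 = 40% of adults and 4 × 80 / 800 = 40% of children. With a flare rate f in the other arms, the withhold arms reach a pooled 30% only at (0.30 − 0.6f) / 0.4, which is 75% for f = 0, 67.5% for f = 5% and 60% for f = 10%.

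The trigger is therefore an aggregate safeguard. It does not bring a single hospitalised flare to the sponsor within a day.

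**The case against.** The strongest reply is that Section 12.4.2 is a recording rule and does not redefine an AE. Section 12.2.1 still counts any untoward medical occurrence, Section 12.4.1 collects SAEs from Day 1 to the end of participation, Section 12.5.2 asks for all SAEs whatever their relationship, and no sentence exempts a flare with a serious outcome. A site could properly report one. This stands, and it means that the text is ambiguous rather than a clear exemption. It does not remove the problem. If a serious flare is not an SAE, there is a reporting gap; if it is one, 12.4.2 contradicts 12.5.2. Either way sites have no instruction that settles it.

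A reader might go further in several ways that the documents do not support:

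- *That flares are never AEs, or that every serious flare is lost.* The solicited-AE route covers the first 7 days.
- *That flares appear only on eCRFs and in six-monthly DSMB listings.* Severe flare within 12 weeks is an ad hoc DSMB trigger in both populations (12.8.2.2). If the DSMB has not met within 2 weeks, new consent and randomisation stop (11.5). Section 12.8.2.1 adds event-driven review. Flares are secondary endpoints (3.3) with planned summaries (13.4.4; SAP 8.3.7), and SAP 9.3 lists all deaths with cause.
- *That a planned SAE comparison of withhold with continue is biased.* The planned contrasts in 13.4.4 concern vaccine response. Safety is summarised descriptively, and flare has its own endpoints.
- *That the SSc severe-flare definition shows hospitalised flares are expected.* Hospitalisation is one of several alternatives in that definition and says nothing about frequency.

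**Conclusion.** The point holds as a gap and an inconsistency in reporting. Followed as written, Section 12.4.2 leaves a serious flare of the qualifying disease, once the 7-day window has closed, outside the SAE endpoint, the 24-hour route and VAERS reporting. Flares of a secondary disease, by contrast, are AEs of every grade. Within the 7 days, 12.4.2 and 12.2.1.3 with 12.5.1 give opposite instructions.

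This rests on reading the exclusion in 12.4.2 literally and the SAE definition as a subset of AEs. Its size in events is unknown. Flares remain under safety oversight; what is missing is expedited reporting of individual cases and a consistent SAE count. The matter deserves an amendment because it bears on the one harm that the protocol names for its own intervention.

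**What to change.** Add to Section 12.4.2 that a flare or relapse meeting any criterion in 12.2.6 is reported as an SAE under 12.5.2, in addition to the disease-specific eCRF. Reconcile 12.2.1.3, 12.2.5, 12.5.1 and 12.5.2 with that sentence. In SAP Section 9.3, show SAEs descriptively with and without flares of the qualifying disease, by IS plan in Cohorts A and B and by arm elsewhere.

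This changes reporting only and leaves clinical management as it is. It costs a few more SAE forms at sites, one more table display, and SAE counts that look somewhat higher. For participants already followed, the display can include earlier serious flares only if the disease eCRFs recorded the outcome, which the documents do not show.

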12.4.3 Collecting Adverse Events

Adverse events (including SAEs) may be discovered through any of these methods:

- Observing the participant.
- Interviewing the participant [e.g., using a checklist, structured questioning, diary, etc.].
- Receiving an unsolicited complaint from the participant.
- In addition, an abnormal value or result from a clinical or laboratory evaluation can also indicate an AE, as defined in Section 12.3 Grading and Attribution of Adverse Events.

12.4.4 Recording Adverse Events

AEs will be recorded on the clinic's progress notes or other source documents in the participant's chart.

Once recorded, an AE/SAE will be followed until it resolves with or without sequelae, or until the end of study participation. For AEs where an abnormal value or result of a clinical or laboratory evaluation is observed (see Section 12.3.1 Grading Criteria), resolution is defined as the first value post abnormality that is in the normal range (Grade 0).

12.5 Reporting Adverse Events and Serious Adverse Events to Sponsor (DAIT/NIAID)

12.5.1 Reporting Adverse Events

This section describes the responsibilities of site investigators to report AEs to the Sponsor (DAIT/NIAID) via the DAIT-SACCC.

Sites are responsible for ensuring the participant completion of the 7-day Vaccine Reaction Diary and assisting participants with entry of all Vaccine Reaction Diary data into the electronic e-Diary in the MyOwnMed portal, if required.

Investigators are responsible for reporting solicited AEs in electronic data capture (EDC) in the following special cases:

- If a solicited AE is also an SAE or MAAE, it must be entered in EDC to capture additional information about the event.

- If a solicited AE, previously reported in MyOwnMed, is found to be ongoing at Day 7 (post vaccination), the solicited AE must be entered in EDC so it can be followed to resolution, with or without sequelae.
- Unsolicited AEs (unrelated to reactogenicity) that are entered into the Vaccine Reaction Diary and are also identified during the Week 1 visit are to be reported in EDC and graded according to the criteria defined in Section 12.3.1 Grading Criteria.

All grade ≥ 1 diagnoses of COVID-19 disease confirmed by molecular COVID-19 testing (or alternative test per institutional standards) will be reported to the Sponsor as AEs.

All MAAE, NOCMC, AESIs, and SAEs (listed in Section 12.4 Collection and Recording of Adverse Events) will be reported until the end of the study. Unless otherwise noted below in Section 12.5.2 Reporting Serious Adverse Events, SAEs and AESIs will be reported within 24 hours. Unsolicited AEs, MAAEs, and NOCMCs must be recorded on the appropriate eCRF within 5 days of discovery of the event. Whenever possible, a diagnosis should be provided rather than compilation of signs/symptoms, with grade of the event dictated by highest grade of the sign/symptom component.

12.5.2 Reporting Serious Adverse Events

This section describes the responsibilities of the site investigator to report SAEs and AESIs to the sponsor via the eCRF. Timely reporting of AEs is required by 21 CFR and ICH E6 R2 guidelines.

Site investigators will report all SAEs (see Section 12.2.6 Serious Adverse Event (SAE)) and AESIs (see Section 12.2.5 Adverse Events of Special Interest), regardless of relationship or expectedness within 24 hours of discovering the event.

For SAEs and AESIs, all requested information on the AE/SAE eCRF will be provided. However, unavailable details of the event will not delay submission of the known information. As additional details become available, the AE/SAE eCRF will be updated and submitted.

When a site investigator identifies an SAE or AESI specified above, he or she must notify DAIT/NIAID via the DAIT-SACCC within 24 hours. Site investigators are to report these events on the SAE eCRF in EDC. Should EDC become unavailable/inaccessible, the site investigator should notify DAIT/NIAID via the DAIT-SACCC email at [contact]. This email can serve as the initial notification; however, within the next business day, the SAE eCRF must be completed.

All requested information on the SAE eCRF should be provided. Unavailable details of the event at time of initial report should not delay submission of known information. The initial report should include at a minimum: AE term, relationship to vaccine, and reason why event is serious (per definitions). Supplementary CRF pages including medical history, concomitant medications, demographics, study drug administration, and death must be provided. As additional details become available, the SAE eCRF should be updated and submitted. Each SAE or AESI must be signed by the investigator in the EDC system at the time of initial submission and upon SAE or AESI closure. If an SAE or AESI is determined to require an expedited report to a Health Authority, then the SAE or AESI will be signed by the investigator on a more frequent basis. With each iteration of the form, the investigator (or designated sub-investigator) must sign the form electronically.

For additional information regarding SAE reporting, contact Rho Product Safety (DAIT-SACCC):

12.5.3 Reporting to Health Authority

After an AE requiring 24 hour reporting (per Section 12.5.2 Reporting Serious Adverse Events) is submitted by the site investigator and assessed by DAIT/NIAID, there are 2 options for DAIT/NIAID to report the AE to the appropriate health authorities (Annual Reporting and Expedited Reporting).

12.5.3.1 Annual Reporting

Per 21 CFR 312.33, DAIT/NIAID will include in the Investigational New Drug Application (IND) Annual Report to FDA all AEs classified as:

- Serious, expected, SARs (see Section 12.2.1.1 Suspected Adverse Reaction (SAR) and Section 12.5.2 Reporting Serious Adverse Events).
- Serious and not a SAR (see Section 12.2.1.3 Solicited Adverse Events (Reactogenicity)).
- Pregnancies.

Note that all AEs (not just those requiring 24-hour reporting) will be reported in the IND Annual Report.

12.5.3.2 Expedited Safety Reporting

This option, with 2 possible categories, applies if the AE is classified as one of the following:

Category 1: Serious and unexpected suspected adverse reaction [SUSAR] (see Section 12.2.1.1 Suspected Adverse Reaction (SAR) and Section 12.2.1.2 Unexpected Adverse Event or Unexpected Suspected Adverse Reaction and 21 CFR 312.32(c)(1)i).

The sponsor shall report any SAR that is both serious and unexpected. The sponsor shall report an AE as a SAR only if there is evidence to suggest a causal relationship between the study drug and the AE, such as:

- A single occurrence of an event that is uncommon and known to be strongly associated with drug exposure (e.g., angioedema, hepatic injury, or Stevens-Johnson Syndrome);
- One or more occurrences of an event that is not commonly associated with drug exposure but is otherwise uncommon in the population exposed to the drug (e.g., tendon rupture);
- An aggregate analysis of specific events observed in a clinical trial (such as known consequences of the underlying disease or condition under investigation or other events that commonly occur in the study population independent of drug therapy) that indicates those events occur more frequently in the drug treatment group than in a concurrent or historical control group.

Category 2: Any findings from studies that suggest a significant human risk

The sponsor shall report any findings from other epidemiological studies, analyses of AEs within the current study or pooled analysis across clinical studies or animal or in vitro testing (e.g., mutagenicity, teratogenicity, carcinogenicity) that suggest a significant risk in humans exposed to the drug that would result in a safety-related change in the protocol, informed consent, and investigator brochure or package insert or other aspects of the overall conduct of the study.

DAIT/NIAID shall notify the FDA and all participating investigators of expedited Safety Reports within 15 calendar days; unexpected fatal or immediately life-threatening suspected adverse reaction(s) shall be reported as soon as possible or within 7 calendar days.

